Title: Improving Asthma Care Together (IMPACT): A Shared Management Pilot Study

NCT #: NCT04908384

Document Date: 03/19/2020

Statistical Analysis Plan

Data Analysis.

Feasibility. Eligibility, enrollment, and retention (number who complete study) data will be summarized in a study flowchart. A priori feasibility benchmarks include $\geq 60\%$ recruitment (eligible dyads who enroll) and $\geq 80\%$ retention; these benchmarks are based on our previous research (80% recruitment, 86% retention) and similar studies.¹⁰⁶⁻¹¹¹ Study withdrawal reasons and timing will also be reported.

Acceptability. Participants will rate IMPACT acceptability via Acceptability of Intervention (AIM) survey and semi-structured interview. The a priori acceptability benchmark will be $\geq 60\%$ of participants rating IMPACT as acceptable (4 or 5 on AIM, table 3).^{106-108,111} Additional participant acceptability feedback will be documented via an exit interview. Quantitative data will be summarized using descriptive statistics whereas qualitative data will undergo thematic analysis, described above.

Analysis of the primary outcomes (asthma responsibility score, self-efficacy). Descriptive summaries of de-identified data will be transferred into SPSS 24 (IBM Corp, Armonk, NY) for analyses. Distributions of interval and ratio level variables will be checked for normality and transformed as necessary. We will compare characteristics of those who completed the study to those who did not to inform the generalizability of findings. We expect an increase in asthma management responsibility scores and increased dyadic interdependence (i.e. nonindependence of scores between dyads)¹⁰³ between parent and child-reported outcomes over time in the intervention group, suggesting true shared management.

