Secondary outcome analyses will use mixed model ANCOVAs to assess whether the primary outcome variable means, adjusted for baseline scores, differ between intervention and control groups. We predict a group x time interaction such that shared management and health outcome variables (asthma responsibility score, self-efficacy, medication adherence, control, QOL) will increase to a greater extent in the intervention group. Also pursuant to Aim 2, the dyadic effect of the intervention will be tested with the Actor-Partner Interdependence Model^{103,112} using structural equation modeling with full information maximum likelihood estimation (FIML). First, the pattern of missing data will be tested to determine if it is missing at random. The FIML method is superior to listwise deletion of missing data points in terms of producing less biased estimates. Next, intraclass correlations (ICC) will be examined for parent and child asthma responsibility, self-efficacy, and general health scores. The APIM produces estimates of actor effects (Person A's pretest \rightarrow Person A's posttest) and partner effects (Person A's pretest \rightarrow Person B's posttest). Actor effects are estimated while controlling for partner effects, and vice versa. In these analyses, dyadic interdependence is indicated by statistically significant **partner effects** (e.g., parent pretest \rightarrow child posttest, controlling for child pretest). Intervention condition will be entered into the model as a dummy coded variable. For each measure taken from both parent and child (i.e., self-efficacy, asthma responsibility) two APIMs will be compared; one in which all of the paths from child variables are constrained equal to their respective paths from the parent variables, and one in which all paths are unconstrained and thus free to vary. Comparison of the fit of these two models indicates whether the effects emanating from the parent are significantly different from those emanating from the child. Parent-child dyads in IMPACT are expected to show stronger **partner effects** than those in the comparison group.

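### The SAP predicts stronger partner effects in IMPACT than in control, but names no model term or comparison that estimates this arm difference

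*SAP*

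**What the plan says.** The relevant text is the second paragraph of the SAP's Data Analysis section.

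- **Purpose.** The SAP states that "the dyadic effect of the intervention will be tested with the Actor-Partner Interdependence Model".
- **Criterion.** A partner effect is the path from one dyad member's pretest to the other member's posttest, adjusted for that other member's own pretest. The SAP says "In these analyses, dyadic interdependence is indicated by statistically significant" partner effects.
- **Treatment arm.** "Intervention condition will be entered into the model as a dummy coded variable".
- **Model comparison.** Two models are fitted for each measure taken from both parent and child: "one in which all of the paths from child variables are constrained equal to their respective paths from the parent variables", and one with all paths free. Its meaning is given as: "Comparison of the fit of these two models indicates whether the effects emanating from the parent are significantly different from those emanating from the child".
- **Prediction.** "Parent-child dyads in IMPACT are expected to show stronger" partner effects than dyads in the comparison group.

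The SAP's paragraph on the primary outcomes also expects interdependence to rise over time in the intervention group, without giving a test. Protocol section 1.5, aim 1d, promises only preliminary testing of interdependence over time and mentions no arm contrast.

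**The concern.** The prediction concerns a difference between arms in a regression path. Estimating it needs a term or constraint that lets the path differ by arm, and none is named. A dummy for arm, taken alone, shifts the adjusted posttest mean and leaves one partner path shared by both arms. The constrained-versus-free comparison is about family role, not arm.

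Nothing else in the plan fills the gap. The predicted group-by-time interaction concerns levels of the outcome variables. The intraclass correlations are to be examined, but no comparison between arms is described.

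The risk is one of interpretation. The SAP treats a significant partner effect as the sign of interdependence, inside a model introduced as the test of the intervention's dyadic effect. A significant pooled path could then be read as support for IMPACT when the path is equal in both arms, or present only in control. Choosing the contrast after seeing the data would make it post hoc.

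**Working it through.** The documents give no alpha, effect size, power or path values for this analysis, so there is no planned figure to reproduce.

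**Inputs from the documents.** 60 dyads in two arms (protocol 1.5). Retention benchmark 80%, and prior experience: "these benchmarks are based on our previous research (80% recruitment, 86% retention) and similar studies" (SAP, Feasibility).

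**Assumed inputs.** 1:1 allocation; standardised, centred pretests; actor path 0.5; residual SD 0.8; parent-child pretest correlation 0.3; two-sided 5% tests.

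**Dyads per arm.** 60/2 = 30. With 86% retention, 60 × 0.86 = 51.6, about 26 per arm. With 80%, 60 × 0.80 = 48, or 24 per arm.

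**Step 1: what each model estimates.** For the child's posttest (the parent's equation mirrors it):

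- Additive: post = b0 + c·arm + a·own pretest + p·partner pretest + error
- With interactions: add d_a·arm × own pretest + d_p·arm × partner pretest

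The prediction is d_p > 0, where d_p is the partner path in IMPACT minus that in control. The additive model has no d_p. With 1:1 allocation and the same pretest distribution in both arms, its p estimates the average of the two arms' paths:

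- 0.4 in IMPACT, 0 in control: (0.4 + 0)/2 = 0.20
- 0 in IMPACT, 0.4 in control: (0 + 0.4)/2 = 0.20
- 0.3 in both: (0.3 + 0.3)/2 = 0.30

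The first two cases are opposite in meaning and give the same pooled path.

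**Step 2: how often each term is significant.** Simulation, 10,000 trials per row, 30 dyads per arm:

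| True partner path, IMPACT / control | Mean pooled path | Pooled path significant | Arm dummy significant | Arm × partner term significant |
|---|---|---|---|---|
| 0.4 / 0 | 0.20 | about 40% | about 5% | about 40% |
| 0 / 0.4 | 0.20 | about 41% | about 5% | about 40% (negative sign) |
| 0.3 / 0.3 | 0.30 | about 75% | about 5% | about 5% |

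The dummy stays at its null rate throughout, so it carries no information on the partner-path difference. The interaction term recovers that difference: its mean is about 0.40 in the first row.

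**Step 3: precision of the arm difference.** In the unconstrained model both equations share the same regressors, so single-equation estimates equal the joint maximum-likelihood ones. A close approximation to the median 95% CI half-width, with n dyads per arm, is t × SD × √(2/[(n − 3)(1 − r²)]), with t on 2n − 6 degrees of freedom:

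- n = 30: 2.005 × 0.8 × √(2/(27 × 0.91)) = 0.46
- n = 26: 2.013 × 0.8 × √(2/(23 × 0.91)) = 0.50
- n = 24: 2.018 × 0.8 × √(2/(21 × 0.91)) = 0.52

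Simulated medians agree. Simulated power for a path difference of 0.4 is about 40%, 36% and 33% respectively. For a difference of 0.2 it is 12–14%.

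**Step 4: sensitivity at 30 per arm**, over residual SD 0.6–1.0 and pretest correlation 0.1–0.5:

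- pooled path significant when the 0.4 effect is in control alone: 24–63%
- pooled path significant when it is 0.3 in both arms: 48–95%
- interaction power for a difference of 0.4: 24–67%
- CI half-width: 0.33–0.63

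**The case against.** The strongest reply is that the SAP does not say the dummy enters as a main effect only. A dummy is also the first step in building a product term, and the authors may have intended one. That is possible, and it makes the pooled-path figures conditional on a literal reading. But the SAP names no product term, and an analyst following the text would have no instruction to fit one. That the test is unspecified holds on either reading.

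Four qualifications stand:

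- **Role constraint.** The precision figures above are for the unconstrained model. If paths are set equal across parent and child, and that equality is true, the half-width at 30 per arm falls to about 0.30–0.32 and power for a 0.4 difference rises to about 69–73%.
- **Enrolment.** Protocol section 2.8 lists 65 children and 65 parents to allow for attrition. If 65 dyads enrol, 65 × 0.86 = 55.9 and 65 × 0.80 = 52, about 28 and 26 per arm instead of 26 and 24. The change is small.
- **Importance.** This is an exploratory analysis in a pilot. The feasibility and acceptability benchmarks and the comparisons of outcome means do not use it.
- **Reporting.** The documents set no reporting rule for this model. The risk of misreading comes from the SAP's description of the model's purpose, not from a stated reporting plan.

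None of these supplies the missing contrast.

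**Conclusion.** The concern holds. The SAP states a between-arm hypothesis about partner paths and specifies no estimate of the between-arm difference. Under the literal, additive reading, a significant partner path can neither support nor contradict the prediction. That conclusion is structural and does not depend on the assumed values.

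The percentages do depend on them: allocation ratio, path sizes, residual SD and pretest correlation are all assumptions. Even the correct contrast will be imprecise at this sample size, so it can be described but not settled. This should be fixed because the repair is cheap; it does not threaten the trial's main feasibility conclusions.

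**What to change.** Name the contrast in the SAP in one of two ways:

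1. Add arm × own-pretest and arm × partner-pretest terms to each equation; or
2. Fit a two-group actor-partner model and compare partner paths free across arms with partner paths equal across arms.

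Report each arm's partner path and the arm difference with its 95% CI, labelled exploratory, as the result that addresses the prediction. State that a pooled partner effect is not evidence of an intervention effect. A path that is significant in one arm and not in the other should not be used in place of the estimated difference.

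The parent-versus-child comparison can stay. If role-constrained estimates of the arm difference are also reported, say that they assume equal paths for parent and child.

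**Cost.** About two sentences in the SAP and no new data. Option 1 adds one fit per measure (asthma responsibility, self-efficacy) and option 2 adds two. If the arm terms are also carried into the parent-versus-child comparison, both of its models need refitting. The drawback is a wide interval, about ±0.46 to ±0.52 in the unconstrained model under the base assumptions, so the result should be presented as an estimate and not as a decisive test.

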1. Determine the feasibility, acceptability and initial efficacy of IMPACT with 60 parent-child dyads in an eight-week pilot randomized controlled trial (RCT).

- a. We will use a priori benchmarks to determine the feasibility of IMPACT based on study eligibility, enrollment, and retention.
- b. Acceptability of IMPACT features and engagement will be determined via exit surveys and semi-structured interviews.
- c. Preliminary effect sizes compared to control will be reported on primary outcomes (asthma responsibility, self-efficacy) and secondary outcomes (medication adherence, asthma control and quality of life).
- d. We will also conduct preliminary testing of dyadic interdependence of asthma responsibility over time.

1.6 Study design. Provide a one-sentence description of the general study design and/or type of methodology.

Your answer will help HSD in assigning applications to reviewers and in managing workload. Examples: a longitudinal observational study; a double-blind, placebo-controlled randomized study; ethnographic interviews; web scraping from a convenience sample of blogs; medical record review; coordinating center for a multi-site study.

This study will use a randomized controlled trial design with two parallel study arms, intervention and control (usual care)

1.7 Intent. Check all the descriptors that apply to your activity. You must place an "X" in at least one box.

This question is essential for ensuring that your application is correctly reviewed. Please read each option carefully.

Descriptor
 1. Class project or other activity whose purpose is to provide an educational experience for the researcher (for example, to learn about the process or methods of doing research).
 2. Part of an institution, organization, or program's own internal operational monitoring.
 3. Improve the quality of service provided by a specific institution, organization, or program.
 4. Designed to expand the knowledge base of a scientific discipline or other scholarly field of study, and produce results that: 
• Are expected to be applicable to a larger population beyond the site of data collection or the specific subjects studied, or• Are intended to be used to develop, test, or support theories, principles, and statements of relationships, or to inform policy beyond the study.

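### The only parent-versus-child APIM comparison tests actor and partner paths together, so a significant result cannot be attributed to the partner effects that the SAP uses to define interdependence

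*SAP*

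**What the plan says.** The dyadic analysis is in the last paragraph of the SAP's Data Analysis section. It names two kinds of path. The first is introduced by "The APIM produces estimates of actor effects (Person A's pretest" and leads to that same person's posttest. The second, the partner effect, leads from one person's pretest to the other person's posttest. The SAP then says that "dyadic interdependence is indicated by statistically significant" partner effects.

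The parent-versus-child step follows: "For each measure taken from both parent and child (i.e., self-efficacy, asthma responsibility) two APIMs will be compared". One model is "one in which all of the paths from child variables are constrained equal to their respective paths from the parent variables"; the other is "one in which all paths are unconstrained and thus free to vary". The fit comparison, the SAP says, "indicates whether the effects emanating from the parent are significantly different from those emanating from the child".

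Neither document plans a model that constrains only the partner paths or only the actor paths, or says what follows a significant joint result. Protocol section 1.5 sets the size ("initial efficacy of IMPACT with 60 parent-child dyads") and, in aim 1d, describes the dyadic work on asthma responsibility as preliminary.

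**The concern.** An actor path in this model is the stability of one person's own score from pretest to posttest. A partner path is the cross-person effect that the SAP takes as its sign of interdependence. The restricted model equates both pairs together, so a significant loss of fit may come from the actor pair, the partner pair or both, and the SAP gives no way to tell which.

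Suppose parents' questionnaire scores are more stable than those of 7-11-year-olds, while each affects the other equally. The joint comparison can then be significant, and a report could take that as evidence that parents and children differ in how much they affect each other. At stake is the interpretation of how shared management works, which the dyadic aim is meant to inform.

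**Working it through.** **No figure to reproduce.** The documents give no power, alpha or expected path values for this comparison, so it was simulated.

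**Inputs from the documents.** 60 dyads (Protocol 1.5). The SAP's 80% retention benchmark gives 0.80 × 60 = 48 dyads. The 86% retention in earlier work that the SAP cites gives 0.86 × 60 = 51.6, or about 52. A condition dummy is in the model (SAP).

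**Assumed, because the documents are silent.** Alpha 0.05, complete data, and two sets of nuisance values:
- Set A: partner paths 0.2 each, pretest correlation 0.4, residual correlation 0.3, residual SD 0.7.
- Set B: partner paths 0.15 each, pretest correlation 0.3, residual correlation 0.2, standardised paths.

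**Model.**
- Parent post = a_P × parent pre + p_CP × child pre + condition + error
- Child post = a_C × child pre + p_PC × parent pre + condition + error

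The SAP's restricted model sets a_P = a_C and p_CP = p_PC, which is 2 df. The partner-only model sets p_CP = p_PC and leaves a_P and a_C free, which is 1 df. The test statistic is n × (ln|S restricted| − ln|S free|), where S is the residual covariance matrix. It is referred to chi-square: critical value −2 ln(0.05) = 5.99 for 2 df, and 1.96² = 3.84 for 1 df.

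**Set A, partner paths truly equal.** Repeat runs agree within about 2 percentage points.

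| Dyads | Actor paths, parent v child | Joint 2-df rejects | Partner-only rejects |
|---|---|---|---|
| 60 | equal | 5–7% | 6% |
| 60 | 0.55 v 0.45 | 13% | 6% |
| 60 | 0.6 v 0.4 | 33% | 6% |
| 60 | 0.7 v 0.4 | 63% | 6% |
| 52 | 0.7 v 0.4 | 57–59% | 6% |

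A gap of 0.55 v 0.50 gives 8% for the joint test at 60 dyads. Raising the residual SD to 0.9 gives 44% for 0.7 v 0.4 and 10% for 0.6 v 0.5.

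**Set B, partner paths truly equal** (3,000 simulated trials per cell). The partner-only test rejects 6–7% in every row.

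| Actor paths, parent v child | Joint, 60 dyads | Joint, 48 dyads |
|---|---|---|
| 0.5 v 0.5 | 6% | 6% |
| 0.6 v 0.4 | 23% | 22% |
| 0.7 v 0.4 | 49% | 40% |
| 0.7 v 0.3 | 72% | 62% |
| 0.8 v 0.3 | 91% | 86% |

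With both partner paths at zero and actor paths 0.7 v 0.4, the joint test still rejects 45% (60 dyads) and 37% (48 dyads).

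**Can the joint test separate the two sources?** In set B at 60 dyads, a pure stability gap of 0.7 v 0.4 rejects 49% of the time. A real partner gap of 0.05 v 0.35 with equal actor paths of 0.5 rejects 48%. The significance rate is the same for opposite explanations.

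**Is a stability gap documented?** Only internal consistency is given (Protocol 5.4, instrument table). For asthma responsibility it is .84 (parent) and .78 (child). With equal true stability of 0.6, that difference alone moves the joint test only to about 7%. For self-efficacy it is .87 for both. Neither figure is a pre-post correlation.

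**Power of the partner-only test.** For partner paths 0.05 v 0.45 with equal actor paths, under set A: about 74–76%, against 85–87% for the joint test. For 0.05 v 0.35 under set B there is no loss: 49% v 48% at 60 dyads, and 41% for both at 48.

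**The case against.** The strongest reply is that the test does what its sentence says. A parent's pretest predicting the same parent's posttest is an effect that starts from the parent, so the SAP's wording covers actor paths literally. Rejecting when actor paths differ is then a true rejection. This stands: the comparison is a legitimate omnibus test, and it runs near its nominal size when all paths are equal.

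Three stronger readings are tempting, and the documents do not support them.

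- A reader might infer that stability differences will be reported as differences in influence, or that the test will often reject for this reason. The SAP never uses the word influence for this comparison. The frequency depends on a stability gap that the documents do not give; modest gaps yield 8–13%, and the documented reliability difference yields about 7%.
- A reader might infer that partner effects go untested. They do not: each partner path is estimated and tested while adjusting for the actor path. Only the formal contrast between the two partner paths is missing.
- A reader might infer that the trial's conclusions about the intervention are at risk. Feasibility, acceptability and the group comparisons do not use this test. The SAP's own APIM prediction concerns stronger partner effects in the intervention arm, not parents against children.

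What the reply does not answer is the attribution problem. The SAP gives interdependence a partner-path meaning, then draws a single parent-versus-child conclusion from a test that mixes in the actor paths.

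**Conclusion.** The point holds as a limit on interpretation. A significant 2-df result cannot be assigned to the partner effects, and a difference in stability alone can produce it. With equal partner paths and 60 dyads, the joint test rejects about 13% to 63% of the time for assumed actor gaps from 0.55 v 0.45 to 0.7 v 0.4 under set A. Under set B the figures are 23% and 49% for 0.6 v 0.4 and 0.7 v 0.4. The partner-only test stays at about 6% under both sets.

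The algebra is certain; the frequencies are conditional on assumed path values, correlations and residual spread. In a pilot whose dyadic testing is described as preliminary, this is worth correcting because it is cheap, not because it threatens the main results.

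**What to change.** Keep the joint comparison and label it an omnibus test. For each of the two measures (asthma responsibility and self-efficacy), add two nested 1-df comparisons against the free model:

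1. partner paths equal, actor paths free;
2. actor paths equal, partner paths free.

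State in the SAP that any conclusion about parent versus child influence rests on the first comparison only, and that the second describes score stability. Say in advance whether both are run whatever the joint result, and report them as exploratory, since they add tests without a multiplicity rule.

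The cost is 2 constraints × 2 measures = 4 extra model fits and a sentence or two in the SAP; no new data are needed. The downside is that the 1-df partner test can have less power than the joint test (about 74–76% v 85–87% in the one case noted), although the other case simulated showed no loss. With 41–49% power for a partner gap of 0.05 v 0.35 at 48 to 60 dyads, a non-significant partner comparison should not be read as showing equal influence.
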